8.10.2 Treatment Period Visit

Refer to the SoA (Section 1.3) and Administrative and General Procedures (Section 8.1).

8.10.3 Discontinued Participants Continuing to be Monitored in the Study

At any point if a participant discontinues from treatment but continues to be monitored in the study, all of study procedures specified in the SoA may be completed at the discretion of the investigator and with Sponsor agreement. The subset of study procedures completed will be communicated in a PCL.

8.10.4 Poststudy

Participants will be required to return to clinic approximately 14 days after the last dose of study intervention for the poststudy visit. If the poststudy visit occurs less than 14 days after the last dose of study intervention, a subsequent follow-up telephone call should be made at 14 days post the last dose of study intervention to determine if any AEs have occurred since the poststudy clinic visit.

8.10.5 Critical Procedures Based on Study Objectives: Timing of Procedure

For this study, taking the blood sample for MK-1942 is the critical procedure.

At any post-dose time point, the blood sample for MK-1942 needs to be collected as close to the exact time point as possible. All other procedures should be completed as close to the prescribed/scheduled time as possible. Study procedures can be performed prior or after the prescribed/scheduled time.

The order of priority can be changed during the study with joint agreement of the investigator and the Sponsor Clinical Director.

Any nonscheduled procedures required for urgent evaluation of safety concerns take precedence over all routine scheduled procedures.

The following variance in procedure collection times will be permitted.

- PK Collection, as outlined in [Table 10](#).

Table 10 Pharmacokinetic Sample (Blood) Collection Windows

PK Collection	PK Collection Window
0 - <1 hr	5 min
1 - <24 hr	15 min
24 - <48 hr	1 hr
48 - 72 hr	2 hr

- Predose standard safety evaluations:
 - Vital signs within 3 hrs prior to dosing
 - ECGs within 1 hour prior to dosing
 - Laboratory safety tests and physical exam within 24 hrs prior to dosing
- Postdose standard safety evaluations: vital signs, laboratory safety tests, targeted neurological exam, physical exam, and C-SSRS
 - a. <24 hr postdose: may be obtained within 30 minutes before and 1 hr after the stated monitoring time.
 - b. 24 hr - <48 hr postdose: may be obtained within 4 hr of the stated monitoring time.
- Post-dose ECG evaluations
 - <24 hours post-dose: should be taken within 15 minutes of stated recording time.
 - 24 hours post-dose: should be taken within 1 hour of stated recording time.
- Study drug administration: \pm 30 mins of stated administration period (AM, PM) and \pm 30 minutes of previous day's administration times for a given participant.

8.10.6 Study Design/Dosing/Procedures Modifications Permitted Within Protocol Parameters

This is a Phase 1 assessment of MK-1942 in humans, and the PK, PD, and safety profiles of the compound is still being elucidated. This protocol is written with some flexibility to accommodate the inherent dynamic nature of Phase 1 clinical studies. Modifications to the dose, dosing regimen, and/or clinical or laboratory procedures currently outlined may be required to achieve the scientific goals of the study objectives and/or to ensure appropriate safety monitoring of the study participants.

As such, some alterations from the currently outlined dose and/or dosing regimen may be permitted based on newly available data, but the maximum daily dose may not exceed those currently outlined in the protocol.

- Repeat of or decrease in the dose of the study intervention administered in any given period/panel
- Interchange of doses between panels
 - Entire period(s) or panel(s) may be omitted
 - Decrease in the duration (eg, number of days) of study intervention administration
 - Adjustment of the dosing interval (eg, divided doses [BID to QD, QD to BID, or vice versa])
 - Instructions to take study intervention with or without food or drink may also be modified based on newly available data
 - Modification of the PK sample processing and shipping details based on newly available data

The PK sampling scheme currently outlined in the protocol may be modified during the study based on newly available PK data (eg, to obtain data closer to the time of peak plasma concentrations). If indicated, these collected samples may also be assayed in an exploratory manner for metabolites.

Up to additional 50 mL of blood may be drawn for safety and/or PK analyses. The total blood volume withdrawn from any single participant will not exceed the maximum allowable volume during his/her participation in the entire study (Section 8).

The timing of procedures for assessment of safety procedures (eg, VS, ECG, safety laboratory tests, etc.) may be modified during the study based on newly available data. Additional laboratory safety tests may be added to blood samples previously drawn to obtain additional safety information. These changes will not increase the number of study procedures for a given participant during his/her participation in the entire study.

It is understood that the current study may employ some or none of the alterations described above. Any alteration made to this protocol to meet the study objectives must be detailed by the Sponsor in a letter to the Study file and forwarded to the investigator for retention. The letter may be forwarded to the IRB/IEC at the discretion of the investigator.

9 STATISTICAL ANALYSIS PLAN

This section contains a summary of the statistical analyses for this trial. Full detail is in the Statistical Methods (Section 9.6).

9.1 Statistical Analysis Plan Summary

Safety

Summary statistics and plots will be generated for raw laboratory safety tests, ECGs, and/or vital signs as well as for change from baseline, as deemed clinically appropriate. Depending on the safety parameter, the difference from baseline will either be computed on the original scale (raw change from baseline) or on the log scale and back-transformed for reporting (percent change from baseline).

Frequency and severity of subjective reports of AEs over the dosing period will be closely monitored and reported. The counts and frequency of AEs will be summarized by treatment. In addition, posterior probabilities (PP) of the incidence of dizziness, nausea, emesis after co-administration of MK-1942 and donepezil to AD patients that are less than a target rate will be provided. Such analyses may also be provided for other AEs identified during the study. The target rate is determined from the incidence of an AE associated with MK-1942 alone from MK-1942 P004, and the maximum tolerable increase in the incidence of an AE. For example, if the true AE rate of MK-1942 alone is 40% and the maximum tolerable increase in AE incidence associated with MK-1942 + donepezil compared to MK-1942 alone is 20%, the target rate would be 60%. A posterior probability greater than 60% will be considered as tolerable.

Responses to the C-SSRS will be tabulated and the individual score > 0 will be listed. The difference from pre-treatment baseline values will also be determined.

Pharmacokinetics

Model-based PK Summary

Evaluation of the effects of donepezil on the PK of MK-1942 in AD patients

At each dose level, individual values of the plasma C_{max} of MK-1942 on the last day of a titrated treatment regimen after co-administration of MK-1942 with donepezil to AD patients, as well as the C_{max} of MK-1942 after administration of MK-1942 alone to HEV in MK-1942-004 will be natural log transformed and analyzed in an ANOVA model. The model contains one factor for treatment (MK-1942 alone in HEV, MK-1942+donepezil in AD patients).

Ninety percent (90%) CIs will be constructed for GMRs (MK-1942 + donepezil in AD patients/ MK-1942 alone in HEV) from the model after back-transformation. The hypothesis that the plasma C_{max} of MK-1942 determined on the last day of a titrated treatment regimen (Day 21 [28]) when co-administered with donepezil to AD patients is similar to the C_{max} obtained following administration of MK-1942 alone to HEV (MK-1942-004) will be supported if the 90% CI for the true GMR (MK-1942 + donepezil in AD / MK-1942 alone in HEV) is contained within the interval (0.5, 2.0). Ninety-five percent (95%) CIs for the least squares means by treatment will be constructed on the natural log scale and will reference a t-distribution. Exponentiating the least square means and the lower and upper limits of these

confidence intervals will yield estimates for the population geometric means and confidence intervals about the geometric means on the original scale. Similar analyses will be conducted with MK-1942 AUC₀₋₁₂ and C_{trough}.

Evaluation of the effects of MK-1942 on the PK of donepezil in AD patients

Separately for each PK parameter, individual AUC₀₋₂₄ and C_{max} of donepezil after co-administration of MK-1942 and donepezil, or donepezil alone (Day -1) will be natural log transformed and analyzed in linear mixed effect model. The model contains fixed effect for treatment (MK-1942 and donepezil, donepezil alone) and random effect for subject. Ninety-five percent (95%) CIs for the least squares means by treatment will be constructed on the natural log scale and will reference a t-distribution. Ninety percent (90%) CIs will be constructed for the true GMRs (MK-1942 + donepezil / donepezil alone) from the model after back-transformation.

Power

PK:

The estimated pooled, between-subject standard deviations on a log scale for MK-1942 C_{max} on the last day of dosing following administration of 3-mg to 20-mg BID doses of MK-1942 for 5 to 10 days to healthy adults in MK-1942-002 is 0.225. Assuming the standard deviation is 30% higher in AD patients than HEV (ie, the between-subject standard deviation on a log scale for C_{max} is 0.29 in AD patients), if the true GMR (MK-1942+donepezil in AD patients/MK-1942 alone in HEV) is 1.00, with 18 AD patients receiving MK-1942 and donepezil and 6 HEV receiving MK-1942 alone in MK-1942-004, there is a 99% probability that the 90% CI of the GMR will fall within the interval of (0.5, 2.0).

Safety:

With 18 AD patients receiving MK-1942 + donepezil and a target rate of 80%, if the true AE rate following administration of MK-1942 + donepezil in AD patients is 60%, there is a probability of 97% that co-administration of MK-1942 with donepezil is considered safe and tolerable.

9.2 Responsibility for Analyses

The statistical analysis of the data obtained from this study will be conducted by, or under the direct auspices of, the Early Clinical Development Statistics Department in collaboration with the Quantitative Pharmacology and Pharmacometrics Department and Translational Pharmacology Department of the Sponsor.

If changes are made to the statistical analysis plan as outline below after the study has begun, these deviations to the plan will be listed, along with an explanation as to why they occurred, in the Clinical Study Report.

9.3 Hypotheses/Estimation

Hypotheses

- The plasma C_{max} of MK-1942 determined on the last day of a titrated treatment regimen (Day 21 [28]) when co-administered with donepezil to AD patients is similar to the C_{max} obtained following administration of MK-1942 alone to HEV in MK-1942-004. That is, the true GMR (MK-1942 + donepezil in AD / MK-1942 alone in HEV) is contained within the interval (0.5, 2.0).

Estimations

- The GMRs of plasma PK parameters (AUC₀₋₂₄ and C_{max}) for those treated with MK-1942+ donepezil versus donepezil alone in AD patients will be estimated.

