3 HYPOTHESES, OBJECTIVES, AND ENDPOINTS

Hypotheses are aligned with objectives in the Objectives and Endpoints table.

Details of the hypotheses to be tested can be found in Section 9.3.

Objectives	Endpoints
Primary	

Evaluate the safety and tolerability of treatment (MK-1942 co-administered with donepezil) in AD patients with mild-to-moderate cognitive impairment.	
Safety measures (VS, ECGs, clinical chemistry, hematology, urinalysis, targeted neurological exams, Columbia suicide severity rating scale) and Adverse Event reports
Secondary	

Evaluate the effects of donepezil on the PK of MK-1942 in AD patients 
Hypothesis
 
The plasma Cmax of MK-1942 determined on the last day of a titrated treatment regimen (Day 21 [28]) when co-administered with donepezil to AD patients is similar to the Cmax obtained following administration of MK-1942 to HEV from MK-1942-004, Panel C. That is, the true GMR (MK-1942 + donepezil in AD / MK-1942 in HEV) is contained within the interval (0.5, 2.0).	
Cmax, AUC0-12, AUC0-24, Ctrough, Tmax, apparent terminal t1/2, CLss/F, and Vzss/F of MK-1942AUC0-24, Cmax, Ctrough, Tmax for donepezil

Objectives	Endpoints

 Evaluate the effects of MK-1942 on the PK of donepezil in AD patients. Estimation: 
 The true GMRs of plasma PK parameters (AUC₀₋₂₄, C_{max}) for donepezil before and during administration of donepezil + MK-1942 to AD patients will be estimated. 	
Tertiary/Exploratory	

 Evaluate the changes in cognitive function of AD patients by comparing the MMSE-2 and DSST scores obtained at baseline with those from the last day of dosing. Explore the relationship between plasma concentrations of MK-1942 and corrected QT intervals. CCI [REDACTED] Explore the relationships between genetic variation, response to the treatment(s) administered, and mechanisms of disease. Variation across the human genome may be analyzed for association with clinical data collected in the study. 	
 MMSE-2 scores DSST scores QTcF Germline genetic variation

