The plasma PK of MK-1942 following multiple dose co-administration with donepezil will be characterized by determining the C_{max}, T_{max}, C_{trough}, and AUC₀₋₁₂ after the first dose. In addition, C_{max}, T_{max}, C_{trough}, AUC₀₋₁₂, AUC₀₋₂₄, apparent terminal t_{1/2}, CL_{ss}/F, V_{zss}/F and accumulation ratio will be determined at steady state. This will allow doses and dosing regimens in elderly participants with AD to be identified that produce systemic exposures in the predicted efficacious range ^{CCI} [REDACTED] while providing insights into the ability of donepezil to alter the PK of MK-1942.

Similarly, the plasma PK of donepezil following once daily administration will be characterized by determining the C_{max}, T_{max}, and AUC₀₋₂₄ on the day before administration of the first dose of MK-1942 and after 21 (28) days of co-administration. Determining the C_{max} and AUC₀₋₂₄ of donepezil during co-administration with MK-1942 will provide insights into the ability of MK-1942 to alter the PK of donepezil.

Exploratory Endpoints

The Mini-Mental State Exam, edition 2 (MMSE-2) will be administered to AD patients at screening and upon completion of up to 28 days of treatment. The score from the MMSE-2 given at screening will be used as an inclusion criterion, to ensure that AD patients being enrolled fall into the cognitive impairment categories of mild to moderate severity. The MMSE-2 is a 30-point examination evaluating Registration, Orientation to Time, Orientation to Place, Attention, Recall, Language, Repetition, Complex Commands, and Recall tasks. A score between 21 to 26 typically indicates that a subject is experiencing mild cognitive impairment, while scores in the range of 10-20 are indicative of patients with moderate cognitive impairment. This study proposes to enroll individuals with mild to moderate cognitive impairment as indicated by scores between 17 to 26. This range will allow for broader recruitment while reducing the burden on CRU personnel associated with caring for patients with MMSE-2 scores < 17. In addition to its use as a screening tool for identifying

candidate participants as having mild to moderate cognitive impairment, the MMSE-2 will be used as an exploratory endpoint to determine whether the treatment regimen results in any changes from the initial score.

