5.1 Inclusion Criteria

A participant will be eligible for inclusion in the study if the participant:

Type of Participant and Disease Characteristics

1. Have a BMI ≥ 18 and ≤ 35 kg/m², inclusive. See Section 8.3.1 for criteria on rounding to the nearest whole number. BMI = weight (kg)/height (m)².
2. Is in good health based on medical history, physical examination, VS measures and ECG performed prior to randomization.
 - Participants with chronic medical conditions, including but not limited to hypertension, hyperlipidemia, diabetes (Type 1 or 2) or hypothyroidism, which have been well-controlled on a stable dose of medication for the past two months and who are not receiving any proscribed medications for treatment may be enrolled if clinically acceptable to the investigator and Sponsor.

Section 10.8, Appendix 8 provides a table of 12-Lead ECG Abnormality Criteria.

3. Is in good health based on laboratory safety tests obtained at the screening visit. Appendix 10.2 provides a table of laboratory safety tests to be performed. Appendix 10.10 provides an algorithm for the assessment of out of range laboratory values.
4. Have a negative UDS prior to randomization.
5. Report a history of cognitive and functional decline with gradual onset and slow progression for at least one year before Screening, that is either corroborated by an informant who knows the subject well or is documented in medical records.
6. Have a MMSE-2 score ≥ 17 to ≤ 26 at Screening, as confirmed by the investigator. The MMSE-2 should be administered by a certified practitioner alternating the colors (red, blue) of the exam for a given subject to avoid learning effects with repeated administration.

7. Be receiving donepezil (maximum dose: ≥ 10 -mg, ≤ 15 -mg) for symptomatic treatment of cognitive impairment associated with Alzheimer's dementia. The dose level must be stable for at least 1 month prior to screening.

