9.6.2 Pharmacokinetics

Model-based PK Summary

Evaluation of the effects of donepezil on the PK of MK-1942 in AD patients

At each dose level, individual values of the plasma C_{max} of MK-1942 on the last day of a titrated treatment regimen after co-administration with donepezil to AD patients, as well as the C_{max} of MK-1942 after administration of MK-1942 alone to HEV in MK-1942-004 will

be natural log transformed and analyzed in an ANOVA model. The model contains one factor for treatment (MK-1942 alone in HEV, MK-1942+donepezil in AD patients).

Ninety percent (90%) CIs will be constructed for GMRs (MK-1942 + donepezil in AD patients/ MK-1942 alone in HEV) from the model after back-transformation. The hypothesis that the plasma C_{max} of MK-1942 determined on the last day of a titrated treatment regimen (Day 21 [28]) when co-administered with donepezil to AD patients is similar to the C_{max} obtained following administration of MK-1942 alone to HEV (MK-1942-004) will be supported if the 90% CI for the true GMR (MK-1942 + donepezil in AD / MK-1942 alone in HEV) is contained within the interval (0.5, 2.0). Ninety-five percent (95%) CIs for the least squares means by treatment will be constructed on the natural log scale and will reference a t-distribution. Exponentiating the least square means and the lower and upper limits of these confidence intervals will yield estimates for the population geometric means and confidence intervals about the geometric means on the original scale. Similar analyses will be conducted with MK-1942 AUC₀₋₁₂ and C_{trough}.

Evaluation of the effects of MK-1942 on the PK of donepezil in AD patients

Separately for each PK parameter, individual AUC₀₋₂₄ and C_{max} of donepezil when co-administered with MK-1942 or alone (Day -1) will be natural log transformed and analyzed in a linear mixed effects model. The model contains fixed effect for treatment (MK-1942 and donepezil, donepezil alone) and random effect for subject. Ninety-five percent (95%) CIs for the least squares means by treatment will be constructed on the natural log scale and will reference a t-distribution. Ninety percent (90%) CIs will be constructed for the true GMRs (MK-1942 + donepezil / donepezil alone) from the model after back-transformation.

Descriptive Statistics

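### The MK-1942 exposure comparison is labelled as donepezil's effect, but it cannot separate donepezil from Alzheimer's disease and from study

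*Combined protocol and SAP*

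**What the plan says.** **Labels.** The secondary objective in 1.1 and 3 reads "Evaluate the effects of donepezil on the PK of MK-1942 in AD patients". The matching analysis in 9.1 and 9.6.2 is headed "Evaluation of the effects of donepezil on the PK of MK-1942 in AD patients". Section 4.2 says that PK changes resulting from co-administration will be assessed for both drugs. The Pharmacokinetic Endpoints part of 4.2.1 says the MK-1942 parameters will help to identify regimens in elderly AD participants "while providing insights into the ability of donepezil to alter the PK of MK-1942".

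**Contrast.** Section 9.3 states the hypothesis that "the true GMR (MK-1942 + donepezil in AD / MK-1942 alone in HEV) is contained within the interval (0.5, 2.0"). The reference is Cmax "obtained following administration of MK-1942 alone to HEV in MK-1942-004"; the objectives tables in 1.1 and 3 narrow this to Panel C of that study. In 9.6.2, "The model contains one factor for treatment (MK-1942 alone in HEV, MK-1942+donepezil in AD patients"). The hypothesis is supported if the 90% CI lies within (0.5, 2.0).

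**Design.** Inclusion criterion 7 (5.1) requires donepezil of every participant. Table 8 (6.3.1) gives 18 participants MK-1942 and 6 placebo, so no one in this trial receives MK-1942 without donepezil.

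**Power.** Section 9.9 gives 99% for the CI to fall within the bounds at a true GMR of 1.00, with 18 AD patients, 6 HEV and a log-scale SD of 0.29 in AD patients.

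**The concern.** The two levels of the model's single factor differ in three ways at once: donepezil, AD, and study. Any difference in age, site or co-medication between the studies travels with them. The GMR is the product of all these effects, while the objective, the heading and the rationale name only donepezil or co-administration.

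A study report normally answers its objectives in their own words. A CI inside the bounds could then be reported as no relevant effect of donepezil on MK-1942, although an opposing AD or study effect may have offset one. A CI outside the bounds could be reported as an interaction, although AD or study may be the cause. The trial's acronym is DDI, so either result is likely to be cited as interaction evidence.

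**Working it through.** **1. What varies in each comparison**

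| Comparison | Donepezil | Disease | Study |
|---|---|---|---|
| MK-1942 PK: AD patients here v HEV in MK-1942-004 | yes v no | AD v healthy | this trial v MK-1942-004 |
| Donepezil PK: Day -1 v co-administration | yes in both | AD in both | same participants |

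The second row answers the reverse question, what MK-1942 does to donepezil, with a random subject effect (9.6.2). It is not aliased with disease or study. The first row is. Covariate adjustment would not help, because no one in the comparison has AD without donepezil, or donepezil without AD.

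**2. The plan's own figure**

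Inputs (9.9): SD 0.225 in healthy subjects; 0.225 × 1.3 = 0.2925, used as 0.29; n = 18 and 6; bounds 0.5 and 2.0; 90% CI, which is two one-sided 5% tests.

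- With 0.29 in both groups, SE = 0.29 × √(1/18 + 1/6) = 0.137.
- The 95th percentile of t on 22 df is 1.717, so the half-width is 1.717 × 0.137 = 0.235 and exp(0.235) = 1.26.
- An observed GMR from 0.5 × 1.26 = 0.63 to 2.0 / 1.26 = 1.58 is therefore declared similar when the observed SD equals 0.29.
- Simulated power at GMR 1.00 (300,000 trials, pooled variance) is 99.9%. It exceeds 99.9% with SDs 0.29 and 0.225, and is 99.6% with a Welch interval and 0.29 in both groups.

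The stated 99% holds, for the composite GMR.

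**3. What that protects**

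Write GMR = D × P, where D is donepezil's effect on MK-1942 Cmax and P is the combined AD/study effect. The documents give neither, so both are assumed here. The probability of declaring similarity depends only on the product:

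| D | P | GMR | SD 0.29 in both | SD 0.29 / 0.225 |
|---|---|---|---|---|
| 2.0 | 1.0 | 2.00 | 5% | 3% |
| 2.0 | 0.8 | 1.60 | 48% | 51% |
| 2.0 | 0.7 | 1.40 | 81% | 87% |
| 0.5 | 1.25 | 0.625 | 47% | 51% |
| 0.5 | 1.5 | 0.75 | 89% | 94% |
| 1.0 | 1.0 | 1.00 | 99.9% | >99.9% |
| 1.0 | 0.7 | 0.70 | 77% | 83% |
| 1.0 | 1.5 | 1.50 | 65% | 71% |
| 1.0 | 2.0 | 2.00 | 5% | 3% |

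Hand check of the second row: (ln 2 − ln 1.6) / 0.137 − 1.717 is about −0.09, and Φ(−0.09) is about 0.47, against 48% simulated.

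At P = 1.0 the 5% rate applies to donepezil's effect as well as to the composite. At any other P it applies to the composite only.

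**The case against.** **The hypothesis is worded correctly.** A reader might infer that the hypothesis itself credits donepezil. It does not: 9.3 and the decision rule in 9.1 and 9.6.2 name both populations and both treatments. Nor does any text available for review say that a CI inside the bounds shows donepezil has no effect. This stands, and it confines the point to the objective, the heading and the rationale. The 4.2.1 wording is hedged as well; 4.2 is more direct.

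**The reference group is partly matched.** Panel C is healthy elderly, planned on the same 8/15/30/50-mg BID titration with 7 days per step (2.2.3.2, Table 5). Concomitant drugs are reviewed for their potential to alter MK-1942 exposure (5.2, criterion 10). Both limit the gap between groups. Neither separates AD or study from donepezil.

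**Masking needs an opposing effect.** True, and nothing visible shows one. The documents give no ages, sites or co-medications for MK-1942-004, so differences there are possible but not shown. An effect in the same direction would exaggerate an interaction instead.

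**Text is redacted.** Parts of 4.2, 4.3.3, 5.2 and 6.5 are blacked out, and some background pages were not available. A stated assumption or limitation could be there, so I do not claim that the plan has none. Such text would not change what the contrast can estimate.

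**This is a Phase 1 secondary objective, and the composite is useful.** Agreed. Exposure in donepezil-treated AD patients bears directly on regimen choice. That is a reason to keep the comparison and name it correctly.

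**Conclusion.** The point holds for the labels. The plan presents as an effect of donepezil or co-administration a ratio that cannot isolate it. The test, the margin and the 99% power are sound for the composite contrast that 9.3 describes.

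The size depends on an AD/study effect that the documents do not give. With SD 0.29 in both groups, a doubling by donepezil is declared similar about 5%, 48% or 81% of the time as that effect goes from 1.0 to 0.8 to 0.7. With no donepezil effect, similarity is declared about 65% of the time at 1.5 and 5% at 2.0. These figures illustrate sensitivity; they do not predict what will happen.

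A reader might go further and infer that the trial will hide a real interaction. The documents do not support that, because they neither show nor exclude an AD or study effect. What follows is narrower: neither verdict can be read as a statement about donepezil alone.

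**What to change.** 1. In 1.1 and 3 (objective), 9.1 and 9.6.2 (heading), and 4.2 and 4.2.1 (rationale), describe the comparison as *MK-1942 exposure in AD patients on donepezil relative to HEV on MK-1942 alone (MK-1942-004)*.
2. Add to 9.6.2 that a 90% CI within (0.5, 2.0) supports similar exposure in the two settings, and neither estimates donepezil's own effect nor rules out an interaction.
3. Tabulate age, weight, sex and renal function for the two groups, where available.

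Leave the 9.3 hypothesis, the model, the margin and the sample size unchanged. The cost is wording and one table; the downside is a narrower claim. Isolating donepezil's effect would need MK-1942 with and without donepezil in the same population, which is a different design and is not proposed here.
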